5.6.4.6 Secondary Safety Endpoint #6

The statistical analysis of secondary safety endpoint #6 will consist of an estimate of the proportion of patients with any SAE through 12-months. This is defined as any serious adverse event through the 12-month follow-up visit, regardless of attribution. The safety population will be used for this analysis. Missing observations will be excluded.

The proportion will be calculated with subjects as the experimental unit. The numerator of the proportion will be the number of subjects with an SAE and the denominator will be the total number of subjects without a missing observation. The endpoint will be presented with the numerator and denominator, the proportion and its 95% two-sided exact binomial confidence interval.

5.6.4.7 Secondary Safety Endpoint #7

The statistical analysis of secondary safety endpoint #7 will consist of an estimate of the incidence of stroke or TIA at 12-month, 2, 3, 4, and 5-year visits (Visits 11-15). The safety population will be used for this analysis. Missing observations will be excluded.

The numerator of the proportion will be the number of stroke or TIA events and the denominator will be the total number of subject years ($\frac{\# \text{Subjects} \times \text{Visit Month}}{12 \text{ Months}}$) for subjects without a missing observation. The endpoint will be presented through each specified visit for each analysis population with the numerator and denominator, the incidence rate and its 95% two-sided exact Poisson confidence interval.

Statistical Analysis Plan		Page 20 of 22
Sponsor	Study	Version
AtriCure	DEEP Pivotal Study	Version 2.0

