5.3 Endocardial EP Ablation Procedure

All subjects should return between Day 91 – Day 121 to have the Endocardial EP Ablation Procedure performed by the Electrophysiologist. Standard cardiac electrophysiologic techniques will be used for mapping, ablation, and arrhythmia induction.

RF based, irrigated, power controlled, ablation catheters for endocardial lesions must be used for endocardial left sided catheter ablation; no other device should be used for ablation purposes in the left atrium. During ablation, it is recommended that power not exceed 50 watts and 35 watts, if the catheter is perpendicular to the tissue. Refer to the relevant Instructions for Use for further details.

The use of phased array intracardiac ultrasound (ICE) during the procedure is encouraged to guide the transeptal puncture and catheter ablation process.

Note: Transesophageal echocardiography (TEE) is used during the Endocardial EP Ablation Procedure. The transesophageal echocardiography probes should be retracted from the area of ablation prior to energy delivery as a measure to protect the esophagus and other surrounding tissue structures.

Note: The order of the below EP procedure (e.g., right-to-left or left-to-right) may be performed according to institutional practices. However, the electrophysiologist should bear in mind the following:

- Monitoring for cavo-tricuspid isthmus lesion and mitral isthmus lesion re-conduction after 20 minutes or longer following initial lesion creation is required.*
- Heparin shall be administered to maintain an ACT of > 300 seconds prior to any left atrial catheter-based ablation maneuvers.*

Note: electroanatomic mapping is required using Multipolar catheters (e.g., Lasso System)

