9.6.2 Secondary Endpoints – Safety

All secondary safety endpoints are supplemental and intended to provide a more complete picture of the overall safety profile for the DEEP procedure. They will not be tested for labeling purposes.

1. Major surgical events – This will be a composite safety endpoint within 30 days of epicardial surgical procedure, as otherwise defined in the primary safety endpoint.
2. Major catheter events – This will be a composite safety endpoint within 7 days of endocardial catheter procedure, as otherwise defined in the primary safety endpoint.
3. 30-day surgical SAEs - This will include all SAEs that occur within 30 days of the epicardial surgical procedure and that are adjudicated to be related to the device or to the procedure.
4. 12-month DEEP SAEs - This will include all SAEs through the 12-month follow-up visit that are adjudicated to be related to an AtriCure device or to either stage of the DEEP procedure.
5. Unresolved SAEs – This will include all SAEs through the 12-month follow-up visit that are adjudicated to be related to an AtriCure device or to either stage of the DEEP procedure and that are not fully resolved by the 12-month visit. These events shall include any procedure-related deaths, strokes with residual disability, unresolved phrenic nerve damage, or other such events that are adjudicated to have resulted in chronic disability or permanent damage.
6. Any serious adverse event through the 12-month follow-up visit, regardless of attribution.
7. Incidence of stroke or TIA at 12, 24, 36, 48, 60-month visits. The ITT population and the AtriClip effectiveness population will be utilized for analysis of this endpoint.
8. Any esophageal injury that meets all of the following criteria: identified post epicardial ablation, adjudicated by core lab to be a thermal injury with perforation, and related to an AtriCure ablation device, through 30-days post epicardial procedure.

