5.1.2 Study Day

Study day 0 is the date of the index procedure. Day in study will be calculated relative to the index procedure as follows:

$$\text{Study Day} = \text{Assessment Date} - \text{Index Procedure Date}$$

For each subject, duration in study will be based on last study contact date which is the latest date of all follow-up visits, assessments, adverse event onset or resolution, and study exit including date of death.

Duration variables will be calculated as follows:

$$\text{Duration Days} = \text{End Date} - \text{Index Procedure Date}$$

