5.2 Analysis Populations

Intent to treat patient population (ITT): The ITT subject population will include all subjects who have met all inclusion/exclusion criteria and on whom a procedure was attempted (defined as a subject who underwent induction of anesthesia).

Modified intent to treat patient population (mITT): The mITT subject population will include all subjects who attempted the Epicardial Procedure (defined as a subject who underwent induction of anesthesia) and have at least one post-procedure follow-up visit after the 2nd Blanking Period (with the 2nd blanking period defined as the 90-days post Endocardial Ablation Procedure) with non-missing primary effectiveness data.

Safety Population: The safety population will include all enrolled subjects that undergo induction of anesthesia.

Per protocol patient population (PP): The PP patient population will include all subjects who complete both the Epicardial Surgical Ablation Procedure and Endocardial EP Ablation Procedure.

AtriClip Effectiveness population: The AtriClip effectiveness population will include all ITT subjects for whom an attempt (entrance of the AtriClip into the chest wall) is made to place an AtriClip device.

The primary effectiveness analysis will utilize the mITT patient population as defined in this statistical analysis plan. The analysis will be repeated on the ITT and PP patient populations as supportive analyses. Secondary effectiveness analyses will be conducted on the mITT, the ITT and the PP patient populations. All safety analyses will utilize the safety population.

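### The stroke/TIA incidence rate uses a nominal exposure that leaves out the interval between the two procedures and all time from subjects with a missing visit, and the SAP does not define which events are counted

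*SAP*

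**What the plan says.** SAP 5.6.4.7 estimates stroke/TIA incidence through the 12-month and the 2-, 3-, 4- and 5-year visits.

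- **Numerator:** "The numerator of the proportion will be the number of stroke or TIA events". No start date is given, and nothing is said about events in subjects who later leave.
- **Denominator:** the "denominator will be the total number of subject years", defined as number of subjects × visit month / 12 and restricted to subjects without a missing observation.
- **Population and missing data:** "The safety population will be used for this analysis. Missing observations will be excluded".
- **Presentation:** "the incidence rate and its 95% two-sided exact Poisson confidence interval", for each analysis population, although only one is named.

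Other sections set the clock:

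- SAP 5.2: "The safety population will include all enrolled subjects that undergo induction of anesthesia". Protocol 4.2.2 places that induction at the epicardial procedure, and protocol 10.5.1 starts adverse event reporting there.
- Protocol 5.3: "All subjects should return between Day 91 – Day 121 to have the Endocardial EP Ablation Procedure performed".
- Protocol 7.14 and 10.5.2 define Visit 11 as 12 months after the endocardial procedure. Protocol 9.6.1 puts the same visit at about 15 months after clip placement.

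Protocol 9.6.2 assigns a different population to this endpoint: "The ITT population and the AtriClip effectiveness population will be utilized for analysis of this endpoint".

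**The concern.** An incidence rate needs events and exposure from the same people over the same period. Here the population enters at surgery, while the exposure formula credits only the months since the second procedure. A subject with no observation at a visit is credited with nothing at that visit. Someone lost late in year 5 would add zero subject-years to the 60-month rate.

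Some of these losses are built into the design. Under protocol 4.4, subjects who withdraw before the endocardial procedure are followed at least to the 1-month visit and then exit, and subjects converted to sternotomy or thoracotomy exit after 12 months. The losses may also be related to the outcome, since protocol 9.2.1 foresees subjects in whom a safety event rules out the catheter stage.

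This is the only endpoint that reports stroke/TIA incidence through 5 years, and protocol 9.3 lists lower stroke risk among the expected benefits. A reader will take the figure as an annual rate.

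**Working it through.** The documents give no expected stroke/TIA rate or event count, so there is no figure to reproduce. The check compares the SAP formula with person-time counted from surgery.

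**Inputs.** Gap of 91 to 121 days (protocol 5.3); N = 220 treated and about 20% attrition (protocol 9.3). Event counts and the timing of exits are assumptions.

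**1. Effect of the gap, no attrition, events counted from surgery.** Ratio of actual to nominal time = (visit month + gap in months) / visit month. At 12 months this is (365 + 91)/365 = 1.25 to (365 + 121)/365 = 1.33.

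| Visit (months) | Nominal subject-years, N = 220 | From surgery | Ratio |
|---|---|---|---|
| 12 | 220 | 274.8 to 292.9 | 1.25 to 1.33 |
| 24 | 440 | 494.8 to 512.9 | 1.12 to 1.17 |
| 36 | 660 | 714.8 to 732.9 | 1.08 to 1.11 |
| 48 | 880 | 934.8 to 952.9 | 1.06 to 1.08 |
| 60 | 1,100 | 1,154.8 to 1,172.9 | 1.05 to 1.07 |

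With the events fixed, the rate and both exact Poisson limits (chi-square quantiles divided by person-time) are too high by the same ratio.

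**2. Adding attrition at 12 months.** Assume that 20% (44 subjects) leave before Visit 11, on average halfway. Nominal time is 176 subject-years. Actual time is (176 + 44 × 0.5) × 456.25/365.25 = 247.3 for the 91-day gap, or 198 × 486.25/365.25 = 263.6 for 121 days. The ratio is 1.40 to 1.50. It ranges from 1.27 (all leave at day 30, 91-day gap) to 1.66 (all leave just before Visit 11, 121-day gap).

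**3. Illustration with an assumed 4 events by Visit 11, per 100 subject-years (95% CI).**

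| Situation | SAP formula | Actual person-time, 91-day gap | Actual person-time, 121-day gap |
|---|---|---|---|
| No attrition | 1.82 (0.50 to 4.66) | 1.46 (0.40 to 3.73) | 1.37 (0.37 to 3.50) |
| 20% attrition, leavers' events kept | 2.27 (0.62 to 5.82) | 1.62 (0.44 to 4.14) | 1.52 (0.41 to 3.89) |
| 20% attrition, 2 of 4 events in leavers and dropped | 1.14 (0.14 to 4.10) | 1.62 (0.44 to 4.14) | 1.52 (0.41 to 3.89) |

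If only one of the four events is dropped, the SAP formula gives 3/176 = 1.70 per 100, still too high. The sign reverses once the share of events kept falls below 176/247.3 = 0.71 (91-day gap) or 176/263.6 = 0.67 (121-day gap).

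**4. The other event window.** If events are counted only from the endocardial procedure, the gap is absent from both numerator and denominator and its ratio is 1. Strokes at surgery and in the following months are then not counted, although the safety population is defined from surgery.

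**The case against.** The strongest reply is that the SAP leaves the event window open, so no fixed bias can be claimed. That stands. A reader might infer that the 12-month rate is inflated by 25% to 33% outright, but the documents support this only if events count from anesthesia.

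A reader might also infer that subjects who die of stroke are removed together with their events. The SAP does not say so. The restriction to non-missing subjects is attached to the denominator, and a recorded stroke followed by death need not be a missing observation. SAP 5.6.4.5 has the same missing-data sentence and yet explicitly counts procedure-related deaths.

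Third, it is tempting to say that the omitted gap and the dropped leavers offset each other. They need not. Losing only leavers' time pushes the rate up, in the same direction as the gap.

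The 91 to 121 days also do not bound every subject. Protocol 5.2 and 7.4 let the endocardial procedure be brought forward once Visit 4 has passed. At a gap of about 30 days the 12-month ratio is 395/365 = 1.08. Protocol 7.7 allows deferral for thrombus, which lengthens the gap. Subjects converted to open surgery have no catheter procedure, so the gap does not apply to them.

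Finally, SAP 5.6.4 makes the endpoint exploratory with no inference. Peri-procedural stroke and TIA adjudicated as serious and related already enter the primary safety composite, and numerator and denominator will be displayed. All this limits the consequence. None of it makes the stated formula a correct incidence rate for the safety population.

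**Conclusion.** The point holds as a defect in how exposure and the event window are specified. Under neither event window does the formula give a correct incidence rate for the safety population.

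- **Events counted from surgery:** the rate and its limits are overstated by about 25% to 33% at 12 months, 12% to 17% at 24 months and 5% to 7% at 60 months. This assumes on-schedule treatment and no attrition.
- **Events counted from the endocardial procedure:** the gap causes no bias, but peri-surgical events are missing.
- **Attrition:** keeping leavers' events while dropping their time raises the overstatement (1.40 to 1.50 at 12 months, under 20% attrition at mid-interval). Dropping their events as well can turn it into an understatement. The documents do not settle which applies.

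The analysis population is also unresolved between SAP 5.6.4.7 and protocol 9.6.2. A reader might infer that the study's conclusion is at risk. It is not, because success depends only on the two primary endpoints.

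**What to change.** Rewrite SAP 5.6.4.7 as follows:

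1. For every safety-population subject, sum actual person-time from the epicardial procedure date to the earliest of the visit cut-off, death or last contact.
2. Count every stroke or TIA in that same interval, including events in subjects who later die or leave.
3. Keep the exact Poisson interval, computed on that exposure.
4. Reconcile the population with protocol 9.6.2: state whether the ITT and AtriClip effectiveness populations are reported with or in place of the safety population, and name each one.

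SAP 5.1.2 already has most of what is needed: "duration in study will be based on last study contact date", with date of death included. It measures from an index procedure without saying which of the two is meant, so the new text should name the epicardial date. The cost is SAP wording and a small programming change. The dates are already collected, and no new data are required.

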5.6.4.8 Secondary Safety Endpoint #8

The statistical analysis of secondary safety endpoint #8 will consist of an estimate of the proportion of patients with any esophageal injury through 30-days post epicardial procedure. This will include all esophageal injuries that meets all of the following criteria: identified post epicardial ablation, adjudicated by core lab to be a thermal injury with perforation, and related to an AtriCure ablation device. The safety population will be used for this analysis. Missing observations will be excluded.

The proportion will be calculated with subjects as the experimental unit. The numerator of the proportion will be the number of subjects with an esophageal injury and the denominator will be the total number of subjects without a missing observation. The endpoint will be presented with the numerator and denominator, the proportion and its 95% two-sided exact binomial confidence interval.

5.6.5 Secondary Health Economics Endpoints

All health economics endpoints are exploratory in nature; no statistical inference will be performed. Analysis of secondary health economics endpoints will be based on descriptive statistics and nominal two-sided 95% confidence intervals for observed data, with methods as described in section 5.1.1.

5.6.5.1 Secondary Health Economics Endpoint #1

The statistical analysis of secondary health economics endpoint #1 will consist of an estimate of the utilization of cardioversion, defined as the number of cardioversion events (visits) that a subject had in the past 12-month period. This endpoint will be measured at the 12-month, 2, 3, 4, and 5-year (Visits 11-15) follow-up visits. The mITT, ITT and PP populations will be used for this analysis. Missing observations will be excluded.

The numerator of the proportion will be the number of cardioversion events and the denominator will be the total number of subjects without a missing observation. The endpoint will be presented for each specified visit window for each population with the numerator and denominator, the incidence rate and its 95% two-sided exact Poisson confidence interval.

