5.1.1 Descriptive Statistics

Continuous data will be summarized with mean, standard deviation, median, minimum, maximum, and number of evaluable observations. Categorical variables will be summarized with frequency counts and percentages. Confidence intervals may be presented, where appropriate, using the t-distribution for continuous data and Clopper-Pearson Exact method for categorical variables unless specified otherwise.

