5.6.5.2 Secondary Health Economics Endpoint #2

The statistical analysis of secondary health economics endpoint #2 will consist of an estimate of the hospital readmissions for AF, atrial flutter, or atrial tachycardia, defined as the number of readmissions in the past 12-month period. This endpoint will be measured at the 12-month, 2, 3, 4, and 5-year (Visits 11-15) follow-up visits. The mITT, ITT and PP populations will be used for this analysis. Missing observations will be excluded.

The numerator of the proportion will be the number of hospital readmissions and the denominator will be the total number of subjects without a missing observation. The endpoint will be presented for each

Statistical Analysis Plan		Page 21 of 22
Sponsor	Study	Version
AtriCure	DEEP Pivotal Study	Version 2.0

specified visit window for each population with the numerator and denominator, the incidence rate and its 95% two-sided exact Poisson confidence interval.

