5.6.5.3 Secondary Health Economics Endpoint #3

The statistical analysis of secondary health economics endpoint #3 will consist of an estimate of the total length of stay (LOS) for all hospital readmissions for AF, atrial flutter, or atrial tachycardia, defined as the sum of the length of stay for each such visit within the last 12-month period. This endpoint will be measured at the 12-month, 2, 3, 4, and 5-year (Visits 11-15) follow-up visits. The mITT, ITT and PP populations will be used for this analysis. Missing observations will be excluded.

The LOS over the previous 12-months will be evaluated with subjects as the experimental unit. The mean LOS will be presented for each specified visit window for each population with its 95% confidence interval using the t-distribution. The standard deviation, median, minimum, maximum, and number of evaluable observations will also be presented.

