5.6.5.4 Secondary Health Economics Endpoint #4

The statistical analysis of secondary health economics endpoint #4 will consist of an estimate of the incidence of Emergency Room Visits for AF, atrial flutter, or atrial tachycardia, defined as the number of visits in the past 12-month period. This endpoint will be measured at the 12-month, 2, 3, 4, and 5-year (Visits 11-15) follow-up visits. The mITT, ITT and PP populations will be used for this analysis. Missing observations will be excluded.

The numerator of the proportion will be the number of emergency rooms visits and the denominator will be the total number of subjects without a missing observation. The endpoint will be presented for each specified visit window for each population with the numerator and denominator, the incidence rate and its 95% two-sided exact Poisson confidence interval.

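### The exact Poisson intervals for cardioversions, readmissions and ER visits make no allowance for event rates that differ between subjects, so they are probably somewhat too narrow.

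*SAP*

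**What the plan says.** SAP 5.6.5.1 treats cardioversion as a per-subject count, "defined as the number of cardioversion events (visits) that a subject had in the past 12-month period", so one subject can contribute several events. The estimate pools these events over all subjects and divides by how many subjects have data at that visit. The result is reported with "the incidence rate and its 95% two-sided exact Poisson confidence interval".

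SAP 5.6.5.2 and 5.6.5.4 follow the same pattern for readmissions ("The numerator of the proportion will be the number of hospital readmissions") and emergency room visits ("The numerator of the proportion will be the number of emergency rooms visits"), with the same denominator and the same interval. All three are repeated at the 12-month and the 2-, 3-, 4- and 5-year visits in the mITT, ITT and PP populations.

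None of the three sections names a dispersion check, a robust variance, a negative-binomial model or a bootstrap. The general rule in SAP 5.1.1 offers no alternative for counts; it provides for intervals "using the t-distribution for continuous data and Clopper-Pearson Exact method for categorical variables unless specified otherwise". SAP 5.6.5 sets the status of the whole group: "All health economics endpoints are exploratory in nature; no statistical inference will be performed".

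**The concern.** An exact Poisson interval fixes the variance of the total count at its mean. That holds if every subject has the same event rate and events occur independently. If some subjects have much higher rates than others, the total varies more than the Poisson model allows and the interval is too short for its nominal 95% label.

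Unequal rates are plausible here. Readmissions and emergency visits count only when they are for AF, flutter or atrial tachycardia, and cardioversion treats the same arrhythmias. Protocol 9.3 plans on 70% of subjects meeting the 12-month effectiveness endpoint, so utilisation can be expected to concentrate to some degree in the rest. At stake is the stated precision of three descriptive utilisation rates.

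**Working it through.** The plan states no rate, event count, dispersion or interval width for these endpoints, so there is no figure to reproduce. The check asks how the specified interval behaves under stated assumptions.

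**Inputs**
- Interval: exact Poisson, two-sided 95% (SAP 5.6.5.1, 5.6.5.2, 5.6.5.4).
- Number of subjects: n = 200, an assumed value between the 182 required for effectiveness and the maximum of 220 treated (Protocol 9.3).
- Event rate: 0.2 per subject per 12 months (assumed), so 200 × 0.2 = 40 expected events.
- Variance-to-mean ratio v of the per-subject count: 1, 1.5, 2 and 3 (assumed).
- Expected success share: 70% (Protocol 9.3).

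**Step 1: the plan's interval.** For x events the limits are χ²(0.025; 2x)/2 and χ²(0.975; 2x+2)/2. With x = 40 they are 28.6 and 54.5 events, a width of 25.9. Divided by 200, that is 0.143 to 0.272 per subject.

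**Step 2: the interval with dispersion allowed for.** Use x ± 1.96 √(x·v), with width 2 × 1.96 × √(40v). Coverage of the plan's interval is simulated by drawing negative-binomial totals with mean 40 and variance 40v (Poisson when v = 1).

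| v | Adjusted limits (events) | Width | Width relative to 25.9 | Actual coverage of exact Poisson interval |
|---|---|---|---|---|
| 1 | 27.6 to 52.4 | 24.8 | 0.96 | 96% |
| 1.5 | 24.8 to 55.2 | 30.4 | 1.17 | 91% |
| 2 | 22.5 to 57.5 | 35.1 | 1.35 | 86% |
| 3 | 18.5 to 61.5 | 42.9 | 1.66 | 77% |

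The widening is less than √v (1.22, 1.41, 1.73) because the exact interval is already wider than the normal-approximation Poisson interval (25.9 against 24.8).

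**Step 3: which v the protocol's planning figure points to.** Suppose 70% of subjects have no events and 30% have a Poisson count with mean λ. Then:
- mean = 0.3λ
- variance = 0.3λ + 0.3 × 0.7 × λ²
- v = variance / mean = 1 + 0.7λ

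Simulated coverage for n = 200:

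| Mean events per subject | λ = mean / 0.3 | v | Coverage |
|---|---|---|---|
| 0.05 | 0.17 | 1.12 | about 97% |
| 0.1 | 0.33 | 1.23 | about 93% |
| 0.2 | 0.67 | 1.47 | about 91% |

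At 0.2 events per subject the split therefore matches the v = 1.5 row. At 0.05 the built-in conservatism of the exact interval absorbs the extra variance. Reaching v = 2 or 3 under this split would need λ = 1/0.7 = 1.4 or 2/0.7 = 2.9, that is 0.43 or 0.86 events per subject, or further differences among the subjects who have events. The documents give no basis for either.

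**The case against.** The strongest reply is that little depends on these intervals. SAP 5.6.5 makes the endpoints exploratory, calls the intervals nominal and rules out inference; Protocol 9.6.3 also calls them exploratory. The success rule in SAP 5.6 uses only the two primary endpoints. All of this stands and it limits the importance of the point. It does not make a 95% label accurate when the interval covers less often than that.

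Second, a reader might infer that repeat events in one subject invalidate a Poisson interval by themselves. They do not. With a common rate and independent events the interval covers at about 96%, slightly above nominal. The shortfall needs rates that differ between subjects, or clustering, and the documents quantify neither.

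Third, the 70/30 split is only a loose guide. The look-back at the 12-month visit covers the past 12 months, so it takes in the second blanking period and the AAD optimisation period. Arrhythmia then is not a failure, and cardioversion is at the physician's discretion (Protocol 7.8, 7.11, 7.12). Some eventual successes will therefore have events. That softens the split, but it does not make rates equal across subjects.

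Fourth, a reader might call the SAP inconsistent because it analyses length of stay by subject ("The LOS over the previous 12-months will be evaluated with subjects as the experimental unit"). That goes too far. Length of stay is a continuous total and receives the default t interval of SAP 5.1.1, while the three counts share the Poisson convention also used for stroke or TIA in SAP 5.6.4.7. The contrast shows only that a subject-level analysis is already familiar to the plan.

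**Conclusion.** The point holds in conditional form. The three sections specify an interval that is valid only if subjects share one event rate with independent events, and they offer nothing to fall back on if that fails. Unequal rates are likely given the planned success rate, so the intervals are probably too narrow.

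The best-anchored illustration is coverage of about 91% instead of 95%, with an adjusted interval about 17% wider. It rests on an assumed 200 subjects, an assumed 0.2 events per subject and a 70/30 split. The figures of 86% and 77% show what happens at dispersions of 2 and 3; they should not be read as expected values for this trial. At low event rates the problem almost disappears. Point estimates, hypothesis tests and study success are not touched, so this is a minor refinement.

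**What to change.** In SAP 5.6.5.1, 5.6.5.2 and 5.6.5.4, replace the exact Poisson interval with mean events per subject and one of the following, named in advance: a Poisson rate with robust (subject-level) variance, a negative-binomial interval, or a subject-level bootstrap. A table of the number of subjects with 0, 1, 2 or more events would let readers see the dispersion directly. A visit with zero events gives these methods nothing to work with, so the exact Poisson limit can be kept for that case.

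The cost is a wording change before analysis, for which SAP section 6 already provides, and somewhat wider intervals. No new data are needed. If overdispersion turns out to be negligible, the reported intervals will be close to those now planned.
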